#### MTN-003B

# Bone Mineral Density Substudy

## LIST OF ABBREVIATIONS AND ACRONYMS

DXA DMPA	adverse event acquired immunodeficiency syndrome area under curve bone mineral density body mass index bone-specific alkaline phosphatase C-terminal telopeptide of type 1 collagen Community Working Group Division of AIDS DAIDS Protocol Registration Office dual energy x-ray absorptiometry depot medroxyprogesterone acetate
DSMB	Data and Safety Monitoring Board
EAE	expedited adverse event Ethics Committee
EC ETV	Early Termination Visit
FDA	(United States) Food and Drug Administration
FTC	emtricitabine
FTC/TDF	emtricitabine/tenofovir disoproxil fumarate
GEE	generalized estimating equation
HIV	human immunodeficiency virus
IND	investigational new drug
loR	Investigator of Record
IRB	Institutional Review Board
LDMS	Laboratory Data Management System
mSv	millisievert
MTN	Microbicide Trials Network
NIAID	National Institute of Allergy and Infectious Diseases
NIH	(United States) National Institutes of Health
NL	network laboratory
P1NP	N-propeptide of type 1 collagen
PSRT	Protocol Safety Review Team
PrEP	pre-exposure prophylaxis
PTH	parathyroid hormone
PUEV	Product Use End Visit
RSC	Regulatory Support Center standard deviation
SD SDMC	
SMC	Statistical Data Management Center Study Monitoring Committee
SINC	study monitoring Committee study specific procedures
JUL	study specific procedures

TDF

tenofovir disoproxil fumarate Vaginal and Oral Interventions to Control the Epidemic VOICE

#### MTN-003B

#### Bone Mineral Density Substudy to MTN-003 (VOICE)

#### PROTOCOL SUMMARY

Short Title:	BMD Substudy	
IND Sponsor:	Division of AIDS, NIAID, US NIH	
Chair:	[name], MPH	
Sample Size:	All eligible participants	
Study Population:	Sexually active, HIV-uninfected women 18 to 45 years old who have been randomized to oral study product in MTN-003 [VOICE (Vaginal and Oral Interventions to Control the Epidemic)], and elect participation in the Bone Mineral Density (BMD) Substudy.	
Study Sites:	VOICE Study sites selected by the MTN Executive Committee	
Study Design:	Observational substudy of VOICE	
Study Duration:	Approximately 48 months total. Accrual will require approximately 21 months. Follow-up will continue 12 months after the VOICE Product Use End Visit (PUEV).	

#### **Primary Objective:**

• To compare changes in BMD after one year among VOICE participants receiving oral tenofovir disoproxil fumarate (TDF) and emtricitabine (FTC)/TDF compared with oral placebo.

#### **Primary Endpoints:**

• Total hip and lumbar spine BMD via dual energy x-ray absorptiometry (DXA).

#### Secondary Objectives:

- To describe changes over time in nutritional assessment components among VOICE participants receiving oral study products.
- To compare changes in BMD over the duration of the BMD Substudy among participants receiving oral TDF and FTC/TDF compared with placebo.
- To evaluate changes in BMD in the 12 months following the discontinuation of an oral study product in VOICE.

#### Secondary Endpoints:

- Nutritional assessment components, including height, weight, body mass index (BMI), clinical findings, and dietary history.
- Total hip and lumbar spine BMD via dual energy x-ray absorptiometry (DXA).

## Exploratory Objectives:

- To explore potential mechanisms of BMD changes among VOICE participants receiving oral study products.
- To explore changes in urinary phosphorus excretion in relation to changes in bone density among VOICE participants receiving oral products.

#### **Exploratory Endpoints:**

- Markers of bone turnover and metabolism.
- Ratio of the maximal tubular reabsorption rate of phosphate and the glomerular filtration rate (TmPO4/GFR).

# 1 KEY ROLES

#### **1.1 Protocol Identification**

- Protocol Title: Bone Mineral Density Substudy
- Protocol Number: MTN-003B
- Short Title: BMD Substudy

Date: August 29, 2011

# 2 INTRODUCTION

## 2.1 Vaginal and Oral Interventions to Control the Epidemic (VOICE)

The VOICE Study will simultaneously assess the safety and efficacy of daily dose oral and vaginal formulations of tenofovir (TDF) and oral FTC/TDF in preventing HIV acquisition. The study design of VOICE also allows limited comparisons of effectiveness, safety, adherence, and associated frequency of viral resistance among HIV seroconverters across formulations.

VOICE is a Phase 2B, five-arm, multi-site, randomized, placebo-controlled trial that is double-blinded within each mode of administration, but open-label with respect to the randomly assigned mode of administration (vaginal or oral). Approximately 5000 participants will be randomized to the five study arms in a 1:1:1:1:1 ratio.

While investigators and participants will be aware of randomization to either the oral or vaginal administration of study product, they will be blinded to the specific study products randomly assigned. All participants will complete monthly follow-up visits for a period of 12 to 36 months, and will receive ongoing HIV risk reduction counseling, condoms, and diagnosis and treatment of sexually transmitted infections (STIs) throughout the course of study participation. Participants will also be scheduled for a Termination Visit approximately 8 weeks following completion of their scheduled end-of-study product use.

The BMD Substudy will explore the potential effects of oral study products on BMD in a subset of VOICE participants.

## 2.2 BMD Considerations in VOICE

## 2.2.1 Expected BMD of VOICE Participants

Based on the cross-sectional study of steroidal hormonal contraception and BMD by Petitti et al.—a study that included the UZ-UCSF site participating in the VOICE Study—it is expected that the baseline BMD of VOICE Study participants will be normal, if not higher than average. This study, conducted among women 30 to 34 years of age who were attending family planning clinics in Brazil, China, Egypt, Mexico, Thailand, and Zimbabwe from 1994-1997, indicated that mean BMD (g/cm^2) values ranged from 0.488 at the midshaft ulna and 0.409 at the distal radius in African women to an average of

0.462 at the midshaft ulna and 0.360 at the distal radius in Asian women (values adjusted for study site, age, BMI, years of lactation, years since last lactation stopped, and occupation of partner, except entry itself and colinear variables).

The possible contributory effect of two other modifiers on BMD also requires attention. First, some data indicate a small decrease in BMD from the use of the hormonal contraceptive, depot medroxyprogesterone acetate (DMPA). The difference in BMD among the DMPA users was less than one SD of the mean of the group who never used hormonal contraceptives. In the study by Petitti et al., use of DMPA was associated with a significantly lower adjusted mean BMD at the distal radius as measured by single x-ray absorptiometry. The BMD (g/cm^2) values among women in the DMPA group in the Petitti et al. study, measured 0.465 at the midshaft ulna and 0.369 at the distal radius (adjusted for study site, age, BMI, years of lactation, years since last lactation stopped, and occupation of partner, except entry itself and colinear variables), which is still higher than the BMD values for Asian women. Thus, the observed natural differences between different populations (African versus Asian) were apparently much greater than the differences due to contraceptive method used. It is important to note that data from the HPTN 035 study indicate that approximately 48% of study participants used DMPA and a similar proportion might be expected in the VOICE Study.

Second, breastfeeding may also adversely impact BMD. Given the high frequency of breastfeeding among sub-Saharan African women, VOICE participants might expect a relatively increased risk for BMD loss through this mechanism. However, there are data to indicate that the impact of both DMPA and breastfeeding on bone density, though measurable, is likely to be small and reversible. This is particularly true in women with good baseline bone density, as is the case with this population, thus, the cumulative lifetime risk of BMD loss in such individuals may not be appreciable.

# 2.2.2 Tenofovir

All three active study products in VOICE contain a form of tenofovir, though only two of the active products (oral TDF and oral FTC/TDF) are expected to have significant and consistent systemic absorption of tenofovir. The effects of tenofovir on BMD have been studied in animals and humans. Although clinically significant bone toxicity has not been observed in human trials of tenofovir performed to date, the effects of this drug on bone health in young, pre-menopausal women has not yet been studied and remains of potential concern.

Tenofovir and TDF administered orally in toxicology studies to rats, dogs, and monkeys at exposures (based on AUCs [areas under curves])  $\geq$  6-fold those observed in humans caused bone toxicity. In monkeys bone toxicity was diagnosed as osteomalacia. Osteomalacia observed in some monkeys appeared to be reversible upon dose reduction or discontinuation of tenofovir. In rats and dogs, bone toxicity manifested as reduced BMD. The mechanism(s) underlying bone toxicity is unknown. However, data in humans have been reassuring. Gilead Study 903, which continues to follow men and

women receiving tenofovir as part of an antiretroviral regimen, has reported on bone monitoring for up to six years in this cohort. Observed decreases in spine BMD were statistically significant at week 144 with a mean percentage decrease at the lumbar spine in patients receiving TDF + lamivudine + efavirenz (-2.2  $\pm$  3.9) compared with patients receiving stavudine + lamivudine + efavirenz (-1.0  $\pm$  4.6). Although observed decreases in spine and hip BMD were statistically significant, these percent changes from baseline are not clinically relevant, and no bone fractures related to TDF have been observed.

#### Clinical Monitoring for Bone Health in VOICE

Given the current limitations in our understanding of the effects of oral TDF and FTC/TDF on BMD in healthy women, the VOICE Study team solicited recommendations from an independent consultant with expertise in the area of bone metabolism and measurement of bone loss. These discussions prompted us to undertake standardized clinical monitoring related to impact on bone, including biannual height measurement and active surveillance for fractures in all participants in VOICE. These outcomes are feasible for all sites to monitor and will provide exceedingly valuable data to inform future studies of longer-term tenofovir use in the setting of both PrEP and antiretroviral therapy.

# 2.3 Study Hypothesis

It is hypothesized that use of the VOICE oral study products will not cause a clinically significant decrease in BMD in substudy participants.

## 2.4 Rationale for Study Design

The BMD Substudy will explore the impact of TDF and FTC/TDF on BMD. To measure and interpret this potential impact, participants in the BMD Substudy will undergo measurement of BMD at the spine and hip throughout their participation in the substudy. They will also have blood drawn and stored for possible future testing to evaluate bone turnover (bone resorption and formation) and bone mineral metabolism, and have urine collected and stored for possible future testing of phosphorus and creatinine. The results of these tests will inform our understanding of BMD outcomes. Possible analyses include those listed in Section 7.5, as well as other assays related to bone resorption, formation, and/or metabolism.

## BMD

In a clinical setting, BMD test results are typically compared to the average bone density of young, healthy adult peak bone mass (T-score) and to the average bone density of other people of the same age, sex, and race (Z-score). For women, the classification of osteoporosis using DXA measurements of BMD is currently based on the T-score if they are age 30 or older. For women under age 30, the Z-score is used (comparison to agematched) since peak bone mass has not yet been reached. In the BMD Substudy, we will look for changes in BMD in women taking the oral study products used in VOICE.

#### Bone turnover

Previous investigators have demonstrated that high bone turnover is an independent risk factor for hip fractures in older women. Although it is unlikely that young women will experience fractures, they may experience bone loss, a major endpoint in the substudy. Greenspan and others have previously demonstrated that bone turnover (bone resorption coupled with bone formation) is associated with the rate of bone loss in women.  Markers of bone resorption include CTX (C-terminal telopeptide of type 1 collagen). Markers of bone formation/growth include P1NP (N-propeptide of type 1 collagen) and BSAP (bone-specific alkaline phosphatase). The major objective of the substudy is to examine potential changes in bone mass in women taking the oral study drugs. If there are significant decreases in BMD, it will be important to determine whether this is due to an increase in bone resorption (increase in CTX), a decrease in bone formation (decreased P1NP and BSAP), or possibly an increase in all markers characterized by greater resorption than formation, leading to the loss of bone.

#### Bone mineral metabolism

Persons with vitamin D insufficiency may also demonstrate increased bone resorption. Vitamin D insufficiency and deficiency are more common in those with dark skin (i.e., African Americans compared to Caucasians). It will be critical to examine vitamin D status in these participants to understand the pathophysiology of bone turnover and bone loss. Vitamin D status is assessed by examining levels of 25-hydroxy vitamin D, serum calcium, and parathyroid hormone (PTH). In participants with vitamin D deficiency, PTH levels may be elevated (secondary hyperparathyroidism) with low to normal levels of serum calcium. The BMD Substudy will allow for levels of 25-hydroxy vitamin D to be analyzed in conjunction with parathyroid hormone, permitting the exploration of the pathophysiology of bone mineral metabolism among African women, for whom data are very limited. Storage of samples from baseline and longitudinally will provide the opportunity to document changes in bone mineral metabolism that may result from the oral study medication. Additionally, phosphorus levels (which can be affected in vitamin D deficient states) will be measured on all participants in the VOICE Study; these levels will be available for analysis for the BMD Substudy as well.

TDF has been associated with proximal renal tubular dysfunction and urinary loss of phosphorus. These changes may be mild and not associated with hypophosphatemia since the bone phosphate will compensate for the urinary losses. Collection of urine will allow for the calculation of the ratio of the maximal tubular reabsorption rate of phosphate and the glomerular filtration rate (TmPO4/GFR) as a more sensitive measure of renal tubular dysfunction related to TDF, and may provide additional information about the physiology of any change in BMD.

As nutritional status may have a significant impact on BMD, a nutritional assessment, comprised of anthropometrics (height, weight, and BMI), clinical findings, and dietary history, will also be used to assist in interpretation of the BMD results.

## Bone Mineral Density Changes Over Time

Two studies have reported on the changes in bone mineral density in healthy HIV negative adult men. In both the iPrEx and CDC MSM PrEP studies, healthy men taking tenofovir DF 300 mg daily had a statistically significant loss of bone mineral density of approximately 1% after 24 to 48 weeks compared to placebo. In the iPrEx study, 503 geographically diverse (5 countries) men participated in the BMD substudy. The loss of bone mineral density among participants in the FTC/TDF arm of the iPrEx study was not associated with any clinical harm, as the FTC/TDF (247 randomized to FTC/TDF) and placebo (256 randomized to placebo) participants reported comparable rates of bone fractures. Although these results are reassuring it is important to closely examine the effect of tenofovir in HIV-negative women, who, as previously stated, are exposed to the differential effects on bone density of contraception, breastfeeding, pregnancy, etc., all known to impact bone mineral density.

Limited data suggest that the bone mineral density changes related to tenofovir are reversible after discontinuation of drug in HIV-positive individuals. This has not been studied in HIV-uninfected persons and is critical information for determining the long term effect of a period of oral PrEP, especially for women. MTN-003B is well structured to obtain BMD data after study drug discontinuation, and to compare changes among active drug and placebo participants.

# 3 OBJECTIVES

## Primary Objective:

• To compare changes in BMD after one year among VOICE participants receiving oral TDF and FTC/TDF compared with oral placebo.

## Secondary Objectives:

- To describe changes over time in nutritional assessment components among VOICE participants receiving oral study products.
- To compare changes in BMD over the duration of the BMD Substudy among participants receiving oral TDF and FTC/TDF compared with placebo.
- To evaluate changes in BMD in the 12 months following the discontinuation of an oral study product in VOICE.

## Exploratory Objectives:

- To explore potential mechanisms of BMD changes among VOICE participants receiving oral study products.
- To explore changes in urinary phosphorus excretion in relation to changes in bone density among VOICE participants receiving oral study products.

# 4 STUDY DESIGN

#### 4.1 Identification of Study Design

The BMD Substudy will be a substudy of VOICE. All VOICE participants randomized to oral study product at selected sites will be offered participation in the BMD Substudy and will be accrued, until all eligible participants have been enrolled. Substudy assessments (detailed in Section 7) will be completed at enrollment in the substudy and semiannually thereafter. These assessments will also be completed at the VOICE Product Use End Visit (PUEV) or the BMD Substudy Early Termination Visit (ETV) if either occurs at least 30 days after the last semiannual BMD Substudy visit.

#### 4.2 Summary of Major Endpoints

• Total hip and lumbar spine bone density via DXA

#### 4.3 Description of Study Population

The study population will be comprised of sexually active, HIV-uninfected women 18 to 45 years old who have been randomized to oral study product in VOICE, elect participation in the BMD Substudy, and meet criteria outlined in Section 5.

#### 4.4 Time to Complete Accrual

Accrual is expected to be completed in approximately 21 months.

#### 4.5 Study Groups

The three study groups included in the BMD Substudy are as follows:

- TDF group (TDF 300 mg and FTC/TDF placebo)
- FTC/TDF group (TDF placebo and FTC/TDF 200 mg/300 mg)
- Oral placebo group (TDF placebo and FTC/TDF placebo)

#### 4.6 Expected Duration of Participation

The expected duration of participation in the BMD Substudy is approximately 48 months total. Accrual will require approximately 21 months. Follow-up will continue for 12 months after the VOICE PUEV.

#### 4.7 Sites

This study is open to VOICE Study sites selected by the MTN Executive Committee.

# 5 STUDY POPULATION

#### 5.1 Selection of the Study Population

In addition to the inclusion and exclusion criteria of VOICE, participants must meet criteria below specific to participation in the BMD Substudy.

#### 5.2 Inclusion Criteria

Women must meet all of the following criteria to be eligible for inclusion in the BMD Substudy:

- 1. Randomized to oral study product in VOICE within the past 14 days
- 2. Able and willing to provide written informed consent for participation in the BMD Substudy

#### 5.3 Exclusion Criteria

Women who meet any of the following criteria will be excluded from the BMD Substudy:

- 1. Pregnant at Screening and Enrollment Visit
- 2. Has a medical condition known to affect bone (e.g., hyperparathyroidism, bone cancer) or taking any medication known to affect bone (e.g., glucocorticoids, heparin, warfarin, cyclosporine, cancer drugs, and thyroid hormone).
- 3. Permanently discontinued from oral study product in VOICE prior to the BMD Substudy Screening and Enrollment Visit.
- 4. At enrollment, any other condition that, in the investigator's opinion, would preclude informed consent, make substudy participation unsafe, complicate interpretation of substudy outcome data, or otherwise interfere with achievement of the substudy objectives.

# 6 STUDY PRODUCT

No additional study product considerations are applicable for the BMD Substudy

# 7 STUDY PROCEDURES

VOICE participants at BMD Substudy sites will be offered participation in the BMD Substudy via a separate informed consent process following random assignment in VOICE to oral study product. Eligibility determination and enrollment may take place on the day of random assignment in VOICE or any time up to 13 days after the date of random assignment in VOICE. In addition to study procedures outlined in Section 7 of the VOICE protocol, participants in the BMD Substudy will have the following evaluations and procedures related to the assessment of bone density and bone turnover/metabolism:

- BMD of spine and hip by DXA
- Serum and urine collection and storage for markers of bone turnover, bone mineral metabolism, and urinary phosphorus and creatinine measurements
- Collection of medical history (if not done in VOICE or other study)
- Collection of concomitant medications (if not done in VOICE or other study)
- Collection of contraception history
- Collection of lactation history
- Collection of physical activity history
- Nutrition assessment
  - 1. Anthropometric
    - Measurement of weight
    - Measurement of height
  - 2. Clinical, including assessment of physical signs of malnutrition
  - 3. Dietary, including a food frequency questionnaire that will capture intake of common local foods

Detailed instructions to guide and standardize all study procedures across sites will be provided in the VOICE Study Specific Procedures (SSP) Manual, available at www.mtnstopshiv.org.

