# 7.2 Screening and Enrollment Visit

Eligibility determination and enrollment may take place on the day of random assignment in VOICE, or up to 13 days after the date of random assignment in VOICE.

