#### 7.6 Follow-up Procedures for Participants who Temporarily Hold or Permanently Discontinue Study Product

Participants who temporarily hold or permanently discontinue use of study product will not routinely be withdrawn from this substudy. Rather, every effort will be made to complete all protocol-specified visits and procedures with these participants, except as noted below.

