For evaluating changes in BMD after product use was discontinued, two Student t-tests will be used to compare the percentage change over the year of follow-up without product use in BMD between each of the following: (1) the TDF active arm and placebo oral arm; and, (2) FTC/TDF active arm and placebo oral arm. Analysis for hip and lumbar spine measurements will be done separately. Note that this analysis is more relevant in the case where at least one effect from the use the active oral products on BMD is observed. In that case, it would be worthwhile to investigate if the effect on the BMD is waning after product use is discontinued and eventually returns to its baseline values (i.e. prior to initiation of product use).

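### Baseline scans, serum and urine may be taken up to 13 days after randomization with no stated requirement that they precede first product use, although the plan treats baseline as pre-product

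*Protocol*

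**What the plan says.** Consent and enrollment come after allocation: Section 7 offers the substudy "via a separate informed consent process following random assignment in VOICE to oral study product". The window for eligibility and enrollment is given there as "any time up to 13 days after the date of random assignment in VOICE", and Section 7.2 repeats it ("up to 13 days after the date of random assignment in VOICE"). Inclusion criterion 1 in Section 5.2 words it as "Randomized to oral study product in VOICE within the past 14 days".

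Section 4.1, Table 1 and Section 7.2.3 place the first DXA scan and the first stored serum and urine at this enrollment visit. Neither these sections nor Section 6, which adds no product considerations, ties the measurements to the first dose.

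Exclusion criterion 3 in Section 5.3 bars a woman who has "Permanently discontinued from oral study product in VOICE prior to the BMD Substudy Screening and Enrollment Visit".

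Two places treat baseline as free of drug. Section 10.5, on recovery after product is stopped, asks whether BMD "eventually returns to its baseline values (i.e. prior to initiation of product use". Section 2.4, under bone mineral metabolism, says: "Storage of samples from baseline and longitudinally will provide the opportunity to document changes in bone mineral metabolism". The sentence goes on to attribute such changes to the oral study medication.

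**The concern.** A change from baseline measures the drug effect only if the baseline value is free of it. A woman who starts product at randomization and is first measured on day 13 already carries part of any effect in her baseline. This can happen in the two active arms but not in placebo, so the between-arm difference in change shrinks. The shrinkage is toward no difference, which is also what the team hypothesizes for BMD (Sections 2.3 and 10.3).

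How much this matters depends on how fast the measurement responds. Two weeks is a small part of a year of bone loss. It may be a large part of the response time of a turnover marker or of tubular phosphate handling. Section 2.4 wants TmPO4/GFR because it is a more sensitive measure of changes that may be mild, and Section 7.5 foresees testing the stored specimens if significant BMD changes are seen. That is when a blunted marker contrast would mislead most.

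**Working it through.** **1. Is pre-baseline exposure possible?** Entry runs from day 0 to day 13 after randomization (Sections 7 and 7.2). The first measurements are taken at entry (Sections 4.1 and 7.2.3). No section requires them before the first dose. Exclusion criterion 3 has a purpose only if a woman can already be permanently off product by that visit. So exposure before baseline is allowed by this document and apparently foreseen. Whether it occurs depends on the VOICE protocol.

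**2. The plan's own power figure.** Inputs from Section 10.4: n = 100 per arm, SD = 4.5%, two-sided 5% level, 90% power, detectable difference 2.1%.

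- Standard error of the difference: 4.5 × √(2/100) = 0.636.
- Detectable difference: 0.636 × (1.960 + 1.282) = 2.06% (2.07% with the t distribution).
- Power at 2.1%: Φ(2.1/0.636 − 1.960) = 91.0% (90.7% with the t distribution).

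The stated 2.1% reproduces.

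**3. DXA with a day-13 baseline.** Assume that product starts on the randomization day, every woman enters on day 13, loss is linear, and the one-year scan falls 12 months after product start.

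- Share of the year missed: 13/365 = 3.6%.
- Of a 1% one-year loss: 0.036 × 1% ≈ 0.04 percentage points.
- A true 2.1% difference is seen as 2.1 × (1 − 0.036) ≈ 2.02%. Power is Φ(2.025/0.636 − 1.960) ≈ 89%.

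Section 2.4 cites a loss of about 1% in men after 24 to 48 weeks. If that 1% were reached linearly by week 48 or week 24, the missed part would be 13/336 = 0.04 or 13/168 = 0.08 percentage points. If the one-year scan is instead timed from the start of follow-up, as the sample size text in Section 10.4 words it, a loss that is linear throughout is captured in full.

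**4. Markers and TmPO4/GFR.** The documents give no onset time. Assume that the effect approaches its plateau as 1 − exp(−t/τ), with product started at randomization and τ in days.

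- Share already in a day-13 baseline: 1 − exp(−13/τ).
- Average share if entry is spread evenly over days 0 to 13: 1 − (τ/13) × [1 − exp(−13/τ)].

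| τ (assumed) | Day-13 baseline | Average, even entry |
|---|---|---|
| 14 days | 60% | 35% |
| 28 days | 37% | 20% |
| 90 days | 13% | 7% |

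These shares are the proportion of the plateau effect that change from baseline would miss.

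**5. The length of the window.** The randomization day plus 13 further days makes 14 calendar days. The second footnote to Table 1 counts 14 days inclusively for height and weight, so Sections 5.2, 7 and 7.2 can describe one window.

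**The case against.** The strongest reply is that the first dose belongs to the VOICE protocol and detailed procedures to the VOICE procedures manual. The order of procedures on the randomization day and the date of first use may already be settled there. That stands, and it is why exposure before baseline can be called only possible. It does not explain why this document describes baseline as pre-product without securing it.

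A second reply is that the phrase in Section 10.5 is a parenthesis about recovery, not a definition, and that baseline in practice is the enrollment assessment. This is fair, but the gap between the two is then the thing to reconcile.

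A third is that the marker assays are exploratory and conditional on the DXA findings. This also stands, and it limits the weight of the point.

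Three stronger readings are tempting and not supported:

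- **A reader might infer that the primary comparison is compromised.** Under linear loss it is not. If loss is front-loaded, the shortfall grows: with an assumed half-life of 24 weeks about 7% is missed and power is about 87%; with 4 weeks, about 28% and 67%. These figures need every woman to enter on day 13, and nothing in the documents supports such half-lives.
- **A reader might infer that 13 and 14 days contradict each other.** Counted inclusively they agree, so this is editorial.
- **A reader might infer that exclusion criterion 3 conflicts with Section 7.6**, which says "Participants who temporarily hold or permanently discontinue use of study product will not routinely be withdrawn from this substudy". The first governs entry and the second retention, and the two can differ. The criterion does select on an event after randomization that assigned product could affect. Few permanent stops are to be expected within 13 days, however, and dropping it would bring barely exposed women into the DXA comparison, which also dilutes the effect.

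**Conclusion.** The point holds as a cheap improvement, not as a threat to the primary result. The protocol allows the first scan and specimens up to 13 days after randomization and does not place them before first product use, while Sections 10.5 and 2.4 read baseline as drug-free.

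For DXA the effect is at most about 0.04 percentage points of a 1% one-year loss if linear, against an SD of 4.5% and a detectable difference of 2.1%.

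For markers and TmPO4/GFR, change from baseline could understate the drug effect. The documents do not allow the amount to be fixed. With onset time constants of 14 to 90 days it is about 13% to 60% for a day-13 baseline and about 7% to 35% on average with even entry. These ranges rest on three assumptions that the documents do not state: product starts at randomization, onset is exponential, and the time constants are as chosen.

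**What to change.** - **Section 7.2:** where enrollment is on the day of randomization, require baseline serum, urine and DXA before first product use. For all women, record the date of first product use.
- **Analysis of markers and TmPO4/GFR:** do not treat a specimen taken after first use as a pre-product baseline. Compare follow-up levels between the randomized arms, and analyse change from baseline in women sampled before first use.
- **Section 10.5:** align the description of baseline with this rule.
- **Section 5.2:** word the window as in Sections 7 and 7.2 (editorial).
- **Section 5.3:** exclusion criterion 3 may stay; report by arm the number of women excluded under it.

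The cost is a short amendment and one date on the case report form, if VOICE does not already collect it. The downside is that some women contribute no pre-product marker value, so the change-from-baseline analysis rests on fewer women. The date and the analysis rule remain useful for women already enrolled, provided the date can be recovered.
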